## **STATISTICS**

### **Sample Size and justification**

This is a pilot study as no data are available on the effect of ingested rhubarb on MRI parameters. We will recruit up to 16 participants: in order to gather 2 data sets for feasibility testing and 10 complete data sets for the study itself.

Two-way analysis of variance will be used to assess for any difference between the test meals. Any difference identified will then be explored by direct comparison between meals. The Wilcoxon Signed Rank test for non-parametric paired data will be used.

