### **Objective**

The primary objective is to gather pilot data on the change from baseline in small bowel water content in healthy volunteers after a meal of lettuce in comparison to rhubarb, a stimulant food, and white bread, a food known to promote intestinal water absorption.

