## STUDY DESIGN

### Trial Configuration

This will be a three-period, three-treatment crossover trial with blinding of data analysis.

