### Randomisation and Blinding

All participants will consume all three study meals. The order of consumption will be determined by random sequence generated using the online program [www.randomization.com](http://www.randomization.com). Consumption of each meal will be separated by at least 5 days in order to minimize carryover effects.

It will not be possible to blind participants or researchers to the meal intervention on each

day. MRI images will be coded, anonymized and separated from data on study day intervention. This will allow blind analysis of small bowel water and colon metrics.

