### Expected duration of participant participation

Each participant will be involved for a minimum of 12 days from enrolment. This may be extended, either for patient convenience or to accommodate bookings on the MRI scanner, as long as each study day is separated by at least 5 days.

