### **Assessment of Efficacy**

Primary endpoint	Outcome Measure
Change from baseline in small bowel water content (0 - 2 hours)	Difference between treatment means
Secondary endpoints	Outcome Measure
Difference in T1 relaxation time between fasting baseline and 2 hours postprandial	Average difference between treatment means
Difference in breath hydrogen and methane between fasting baseline and 3 hours postprandial	Average difference between treatment means
Difference in bloating and satiety scores between fasting baseline and 3 hours postprandial	Average difference between treatment means

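### Optional improvement: the plan for this three-period crossover mentions neither balance of meal orders nor a period term; adding both costs little, and the gain depends on a period effect of unknown size

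*Combined protocol and SAP*

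**What the plan says.** - **Design.** Trial Configuration: "This will be a three-period, three-treatment crossover trial with blinding of data analysis". Details of Trial Regimen gives 10 participants.
- **Meal order.** Randomisation and Blinding: "The order of consumption will be determined by random sequence generated using the online program". No block, Latin square or other balance is stated. The one measure against order-related effects is a gap between visits: "Consumption of each meal will be separated by at least 5 days in order to minimize carryover effects".
- **Timing.** Expected duration of participant participation sets a minimum of 12 days and adds: "This may be extended, either for patient convenience or to accommodate bookings on the MRI scanner".
- **Outcome.** The Objective is to "gather pilot data on the change from baseline in small bowel water content in healthy volunteers", comparing lettuce with rhubarb and with bread. Assessment of Efficacy uses the change over 0 to 2 hours and the difference between treatment means. The Study Day timetable has one fasting scan and three post-meal scans.
- **Analysis.** Sample Size and justification: "Two-way analysis of variance will be used to assess for any difference between the test meals". Pairwise comparisons follow: "The Wilcoxon Signed Rank test for non-parametric paired data will be used". Neither that section nor Assessment of Efficacy mentions period, visit order or sequence, and the two ANOVA factors are not named.

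**The concern.** In a three-period crossover each meal is compared across study days, so a change in response over the three days can enter the meal comparison. It can be handled in the design (orders balanced over periods) or in the analysis (a period term). The plan states neither. The likely readings of the ANOVA, participant + meal or meal × time of scan, leave period out, and the Wilcoxon tests cannot adjust for it.

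With 10 people and one order list, chance imbalance can be large. If the response drifts, the drift goes into the error and can move a meal contrast in the list actually used. The pilot exists to supply estimates of these contrasts, so their precision is what is at stake.

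**Working it through.** The plan gives no alpha, SD, effect size or power, so it has no figure to reproduce.

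**Inputs from the documents:** 3 periods, 3 meals, 10 participants, change from same-day baseline, three post-meal scans.

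**Assumed:** 5% alpha; one meal 1.2 SD above the other two, where SD is the within-person SD of the change score; a linear shift *d* in the change score from period 1 to period 3; orders drawn without restriction; the planned ANOVA read as participant + meal on one change score.

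**1. What cancels.** If a period adds *a* to both fasting and post-meal water, (post + *a*) − (fasting + *a*) = post − fasting. Only a shift in the response to the meal remains.

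**2. Degrees of freedom.** 10 × 3 = 30 values. Participant + meal leaves 30 − 10 − 2 = 18 error df; adding period leaves 16. The t value moves from 2.101 to 2.120.

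**3. Imbalance.** With unrestricted orders, 48% of lists put some meal in the same period for 6 or more of the 10, and 14% leave some meal out of a period altogether. With one full block of six sequences plus four of a second, every meal-by-period count is 2 to 4. Chance displacement of the unadjusted lettuce–bread contrast, per 1 SD of shift: unrestricted, mean 0.18 SD and 97.5th percentile 0.50 SD; blocked, mean 0.07 SD and maximum 0.15 SD.

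**4. Interval width.** Period values −*d*/2, 0, +*d*/2 have a within-person sum of squares of *d*²/2 on 2 df. Under random orders they therefore add *d*²/4 to the error variance. The mean 95% half-width for the plan is 0.93 SD with no shift, so:
- *d* = 0.5: 0.93 × √1.0625 = 0.96 SD
- *d* = 1: 0.93 × √1.25 = 1.04 SD

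With blocks and a period term it is 0.94 SD at every shift. The cost of the fix with no shift is √1.017 × 2.120/2.101 = 1.018, because the contrast variance rises 1.7% on average (3.1% at most). Setting 1 + *d*²/4 = 1.018² = 1.036 gives *d* ≈ 0.38. Interpolating the simulated half-widths gives about 0.3.

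**5. Power of the overall meal test.** The noncentrality is 10 × 1.2² × 2/3 = 9.6, giving 0.72 on 2 and 18 df. At *d* = 1 it is 9.6/1.25 = 7.68, giving 0.62. For the fix it is 9.6/1.017 = 9.44 on 2 and 16 df, giving 0.71. Simulation (60,000 trials per cell) agrees:

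| Shift (SD) | As planned | Period term only | Blocks + period |
|---|---|---|---|
| 0 | 0.72 | 0.66 | 0.70–0.71 |
| 0.5 | 0.70 | 0.66 | 0.71 |
| 1 | 0.61–0.62 | 0.66 | 0.71 |
| 2 | 0.41 | 0.66 | 0.71 |

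Blocks without the period term are not enough. The shift then sits in the residual: type I error falls to 2.8% (1 SD) and 0.6% (2 SD), and power to about 0.61 and 0.33. The period term without blocks raises contrast variance by 14% on average. Hence both parts together.

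**6. Type I error depends on the reading of the ANOVA.** With no period effect, participant + meal on one change score holds about 5%. For an ANOVA on the three scans (10 people × 3 meals × 3 scans; assumed variances: participant 0.5–2, study day 1, scan 0.5–1):

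| Analysis | Type I error for meal |
|---|---|
| Meal × time, participant ignored | about 6–19% |
| Participant removed, one pooled residual | about 27–34% |
| Meal tested against meal-by-participant | about 5% |

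**7. Unequal spread.** With assumed SDs of 0.6/1.4/0.8 for bread/rhubarb/lettuce, the pooled-variance 95% interval covers about 99% for lettuce–bread, 93% for rhubarb–bread and 91% for lettuce–rhubarb. The planned participant + meal model gives the same coverage.

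**The case against.** The strongest case against acting is that no period effect is documented and the protocol limits the room for one. Volunteers are healthy, pre-visit restrictions and fasting are the same each time, one scanner is used, images are read blind to meal, and each visit has its own baseline. Below a shift of 0.3–0.4 SD the fix is neutral or slightly worse. The trial is a pilot that claims no power. All of this stands, and it is why the point is an optional improvement.

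It also stands that the comparison column is a model of the plan. The documents do not give the randomisation program's setting. If the list was already balanced, the imbalance and as-planned figures do not apply. Every power figure depends on the assumed 1.2 SD.

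A reader might infer that two factors cannot accommodate participant, meal and period. That goes too far: in a repeated-measures ANOVA the participant is the error stratum, so meal + period within participant is a possible reading, though it is not stated.

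A reader might equally take comfort that any natural reading of the ANOVA holds 5% type I error. Step 6 shows that this is so for participant + meal, or with meal tested against meal-by-participant, and not for the other meal × time versions.

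**Conclusion.** The point holds as a low-cost improvement of optional to moderate priority. The plan states no balance of orders and no period term, and it leaves the ANOVA factors open. Under the stated assumptions the fix loses 1–2 power points with no shift, gains about 1 at 0.5 SD and about 10 at 1 SD. At 1 SD the mean interval half-width falls from 1.04 to 0.94 SD.

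Three stronger conclusions might be drawn and are not supported. The plan is not shown to be systematically biased, since meal order is random. The orders are not shown to be unbalanced, since the documents are silent on this. A benefit is not established, since no period effect is quantified.

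**What to change.** Make both changes together.

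1. **Orders.** Assign meal orders in blocks of the six sequences (for 10 people, one full block plus four sequences of a second). A replacement takes the sequence of the person replaced. If the list is already balanced, say so; only the second part is then needed.
2. **Model.** Analyse one change-from-baseline small bowel water value per study day with participant + period + meal, and name these terms. If all three post-meal scans are modelled, test meal against between-day, within-participant variation. State that the period-adjusted meal contrasts with 95% intervals are the primary estimates and the Wilcoxon tests are supporting.

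If an unbalanced list has already been used, present the period-adjusted model as a sensitivity analysis, because the term alone costs about 6 power points (0.72 to 0.66) when there is no shift.

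**Cost.** Two or three sentences and a regenerated list; no extra participants, visits or scans. Error df fall from 18 to 16, with 1–2 power points and a 1–2% wider interval if there is no drift. The pooled interval assumes similar spread across meals, as the participant + meal model already does, which is a reason to keep the Wilcoxon tests beside it.

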### **Assessment of Efficacy**

Primary endpoint	Outcome Measure
Change from baseline in small bowel water content (0 - 2 hours)	Difference between treatment means
Secondary endpoints	Outcome Measure
Difference in T1 relaxation time between fasting baseline and 2 hours postprandial	Average difference between treatment means
Difference in breath hydrogen and methane between fasting baseline and 3 hours postprandial	Average difference between treatment means
Difference in bloating and satiety scores between fasting baseline and 3 hours postprandial	Average difference between treatment means

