### Primary endpoint

- Small bowel water content (mL), measured by MRI

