### Visits 2 - 4 (Study Days)

On the day before a study day participants will be asked to avoid caffeine (tea, coffee, cola), alcohol, dietary or sports supplements including those containing trace elements. They should also avoid apples, beans, peas, pulses (e.g. lentils) and sweetcorn. They should not eat after 8pm.

On each study day participants should remain nil by mouth apart from essential medicines. They will attend the 1.5T Phillips scanner of the SPMIC as directed by the study team. Once consent and safety of MRI scanning has been confirmed, they will change into surgical scrubs (provided) and undergo fasted assessment: 1) MRI scan; 2) measurement of breath hydrogen (H2) and methane (CH4) by breathing into a gas analyser (GastroCHECK, Bedford, UK); assessment of bloating and satiety symptoms by 100mm visual analogue scale. Further assessments will be staggered between participants so that no two participants have the same assessment timetabled at the same time.

Participants will then consume the test meal assigned for the day. 200mL still water will be provided to drink with the meal. Participants will be given up to 20 minutes to consume each meal. The first post-prandial assessments will be taken immediately after the meal is fully consumed. Further assessments will be made at 30-minute or 60-minute intervals as set out in the figure.

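### Raw change from the fasting scan fixes the baseline slope at 1; prespecifying that scan as a covariate is a cheap and usually safer choice for precision, with a gain the documents cannot size

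*Combined protocol and SAP*

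**What the plan says.** - The Objective section sets out to "gather pilot data on the change from baseline in small bowel water content in healthy volunteers after a meal of lettuce", with rhubarb and white bread as comparators. The Assessment of Efficacy table agrees: the primary row reads "Change from baseline in small bowel water content (0 - 2 hours" and its outcome measure is "Difference between treatment means".
- The Primary endpoint section lists only "Small bowel water content (mL), measured by MRI", without mentioning change.
- Under Sample Size and justification, "Two-way analysis of variance will be used to assess for any difference between the test meals". The factors, the variable and any covariate are not named. Pairwise comparisons follow: "The Wilcoxon Signed Rank test for non-parametric paired data will be used".
- On every study day participants "undergo fasted assessment: 1) MRI scan" before eating, so each meal has its own baseline. The Study Day timetable shows that scan at 0900 and post-meal scans at 1000, 1100 and 1200.
- The design is a three-meal, three-period crossover in random order, with 10 complete data sets planned. It is described as a pilot. No SD, correlation, power or effect size is given.

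**The concern.** A contrast between meals A and B on raw change equals (post A − post B) − 1 × (fasting A − fasting B). The multiplier 1 is imposed by the definition, not estimated. If day-to-day variation in fasting water carries over only partly into the post-meal value, subtracting all of it adds noise. The fasting scan is already collected, and nothing in the plan uses it as a covariate.

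What is at stake is interval width. The main product of this pilot is a set of meal contrasts from 10 people, and how useful they are depends on how tightly they are estimated. A later trial would also need the within-person correlation and SDs, which the plan does not say will be reported.

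**Working it through.** **No figure to reproduce.** The plan of 10 data sets rests on no power calculation, so there is nothing to re-derive.

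**Inputs.** From the documents: 10 people, 3 meals, 3 periods, one fasting scan per meal. Assumed, because the documents do not give them: r (within-person, same-day correlation of fasting and post-meal values) and k (within-person fasting SD ÷ post-meal SD). Errors are taken as normal.

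**Same target.** The fasting scan precedes the meal and meal order is random, so fasting values do not differ systematically by meal. Change and covariate-adjusted contrasts therefore estimate the same difference between meal means.

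**Large-sample variances**, with the post-meal SD set to 1:
- raw change: k² + 1 − 2rk
- adjusted: 1 − r²
- post-meal value alone: 1

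The true slope is r/k. Change and adjusted variances are equal when r = k, that is, when the slope is 1.

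**Allowance for 10 people.** With participant, period and meal fitted, error df = 30 − 1 − 9 − 2 − 2 = 16, or 15 with the covariate. Estimating the slope inflates the adjusted variance by about 1 + 1/14 = 1.0714. The t multipliers are 2.1199 (16 df) and 2.1314 (15 df). The width of an unadjusted interval relative to the adjusted one is the large-sample SE ratio times 2.1199 / (2.1314 × √1.0714) = 0.961.

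Example, k = 1 and r = 0.3: √(1.4/0.91) × 0.961 = 1.240 × 0.961 = 1.19, so raw change is 19% wider.

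Width relative to the adjusted interval:

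| | r = 0.1 | 0.3 | 0.5 | 0.7 | 0.9 |
|---|---|---|---|---|---|
| Raw change, k = 1 | +30% | +19% | +11% | +4% | −1% |
| Raw change, k = 0.75 | +15% | +6% | 0% | −4% | +2% |
| Raw change, k = 0.5 | +4% | −2% | −4% | 0% | +30% |
| Post-meal value alone, any k | −3% | +1% | +11% | +35% | +120% |

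Simulated trials of 10 people agree to within about 1 to 2 points.

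**Downside.** At r = k the adjusted interval is wider on average by 1/0.961 = 1.04, about 4%. That is an average, not a ceiling: at r = k = 0.5, 46% of simulated trials exceeded 4%, and the 95th percentile was 15%. If each pair of meals is modelled separately (8 df against 9), the average cost is about 8%, and the k = 1 row for raw change becomes +25%, +14%, +7%, 0%, −5%.

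**Unequal spread by meal.** Assume post-meal SDs of 0.67 (bread), 1 (lettuce) and 1.5 (rhubarb) times the fasting SD, with r = 0.3, 0.5 and 0.7.
- A common-variance three-meal model with the covariate gave 95% intervals covering about 91% to 93% for lettuce versus rhubarb and about 98% for lettuce versus bread. Raw change in the same kind of model also under-covered lettuce versus rhubarb, at about 92% to 93.5%.
- A paired adjusted regression for lettuce versus rhubarb covered 95.2%, 95.0% and 95.0%.
- In the paired regression, raw change was 26%, 18% and 11% wider for lettuce versus bread, but +4%, −2% and −7% for lettuce versus rhubarb.
- The Wilcoxon test on paired change, lettuce versus rhubarb, kept its type I error at 4.8% to 5.3%.

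**The case against.** The strongest case against is that no defect has been shown. This is a pilot with no powered hypothesis, change from baseline answers the stated objective directly, and choosing a covariate model is a preference. That stands, and it is why the point is an improvement rather than a correction. A reader might infer that the change score biases the meal comparison or invalidates the test. The documents do not support that: order is randomised, every meal has its own baseline, and the raw-change contrast is a valid estimate.

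A reader might also infer that adjustment is bound to narrow the intervals. It is not. The gain rests on r and k, and it vanishes or reverses when r is near k.

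A sharper objection is that the post-meal value alone, which is the literal wording of the Primary endpoint section, already captures the gain. At r up to 0.3 this is right: most of the benefit comes from not subtracting the baseline. At r = 0.5 and above, the post-meal value alone is 11% to 120% wider than the adjusted interval. Of the three options, only the covariate is never far from the best across the assumed grid.

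Three further limits stand. A common-variance adjusted model mis-covers if meals differ in spread, which is plausible because rhubarb is the positive and bread the negative control. The calculations assume normal errors, and skewed volumes were not examined. Finally, the ANOVA's factors are unnamed: if they are meal and time on raw values, the slope argument applies to the endpoint in the efficacy table and not to that model.

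**Conclusion.** The point holds as an optional gain in precision, with medium confidence. Raw change fixes the slope at 1, and nothing in the plan adjusts for a scan that is taken anyway. Over the assumed grid, raw-change intervals range from about 30% wider to about 4% narrower, on average, than adjusted ones. The balance favours the covariate because its average loss is small and its possible gain is not, but the documents cannot say where in that range this trial lies. If rhubarb's spread is larger, the benefit falls mainly on lettuce versus bread.

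The different wordings of the primary endpoint, and the unstated choice between the 2-hour value and a summary of the post-meal scans, need clarifying. They should not be read as evidence of a wrong analysis, since the Objective and the efficacy table agree on change.

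**What to change.** In Sample Size and justification and in the primary row of Assessment of Efficacy, prespecify the meal contrasts and their 95% intervals as baseline-adjusted, using one of two forms chosen in advance:

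1. For each pair of meals, regress the within-person difference in post-meal value on the within-person difference in fasting value; the intercept is the contrast. This form was simulated, without a period term, and held its coverage for lettuce versus rhubarb.
2. Fit one model with participant, period, meal and that day's fasting value, with meal-specific variances written in from the start. This form was not simulated.

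Do not use a common-variance model with a residual check that triggers a switch. Under the unequal spreads above, a Levene test at 5% flagged only about 3% of simulated trials, and coverage after the switch stayed near 92%.

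Keep raw change with the Wilcoxon signed rank test as a sensitivity analysis. Name the fasting scan as the baseline, say which post-meal value is analysed, and match the Primary endpoint line to it. Report the within-person correlation and both SDs for the later trial.

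The cost is a few lines of text and one degree of freedom, with no new data. If the true slope is near 1, intervals are on average about 4% wider in a single three-meal model and about 8% wider in separate pairs, and more in some individual trials.

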### **Hypotheses**

- The test meals will lead to different amounts of post-prandial water in the small bowel
- The test meals will lead to differences in the post-prandial physical form of chyme in the colon
- Meals with higher small bowel water will also induce greater symptoms of bloating, irrespective of markers of fermentation

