### Secondary endpoints

- T1 relaxation time (ms) of the chyme in the ascending colon, measured by MRI
- Breath hydrogen and methane (ppm), measured using GastroCHECK
- Bloating and satiety score, measured using 100mm visual analogue scale

We will also measure gastric volume to confirm passage of the meal into the small bowel.

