### **Feasibility testing**

On a single day two volunteers will undergo testing with the rhubarb meal with scanning every 30 minutes. The aim of this will be to confirm the time course of small bowel water after rhubarb, which is intended to be the positive control. This work will be undertaken under a pre-existing ethics approval G19062014\_SoPA\_SPMMRC: "MR Imaging to evaluate the gastrointestinal fate of foods and beverages". This is for MRI development work in healthy volunteers.

This may lead to modifications of the study day timetable set out below, but will not increase the number of MRI scan sessions undergone by participants. Other assessments, breath tests and symptom scores, are considered a sufficiently light burden that it would be reasonable to add up to 4 additional assessments per day if a longer study day is required.

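### Breath hydrogen and methane: adjust the 3-hour value for that visit's fasting reading instead of subtracting it, and state how the seven post-meal samples are used

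*Combined protocol and SAP*

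**What the plan says.** In the Assessment of Efficacy table the breath endpoint is "Difference in breath hydrogen and methane between fasting baseline and 3 hours postprandial", with the outcome measure "Average difference between treatment means". The primary endpoint in the same table is instead given a window of 0 to 2 hours. The Secondary endpoints list has only "Breath hydrogen and methane (ppm), measured using GastroCHECK", with no time point or summary.

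The Study Day table schedules one fasting breath sample (0900) and seven after the meal, half-hourly from 1000 to 1300. Visits 2 - 4 (Study Days) adds that "The first post-prandial assessments will be taken immediately after the meal is fully consumed", so the 1300 sample is the 3-hour one. Feasibility testing says of breath tests and symptom scores that "it would be reasonable to add up to 4 additional assessments per day if a longer study day is required".

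Sample Size and justification names a two-way analysis of variance without naming its two factors, followed by Wilcoxon signed rank tests between meals. The target is 10 complete data sets.

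**The concern.** Read literally, each participant contributes one number per gas and meal: a single 3-hour reading minus a single fasting reading. Subtraction fixes the weight on the fasting value at one. Unless the two readings track each other closely, that adds fasting noise to the contrast between meals. The other six post-meal readings have no stated role, so a summary of them could be chosen after the data are seen.

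The marker also matters beyond its own row. The third hypothesis is "Meals with higher small bowel water will also induce greater symptoms of bloating, irrespective of markers of fermentation", and an imprecise fermentation marker makes it easier to conclude that fermentation plays no part.

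**Working it through.** **Inputs.** From the Study Day table: seven post-meal samples, of which the endpoint names one. Fasting to 3-hour is 0900 to 1300, which is eight half-hour steps. There are 10 participants and three meals, so 30 values per gas. The documents give no SD, correlation or time course for breath gas, and no figure to reproduce. Assumptions: equal variance s² at every time, and correlation either constant at ρ or decaying as r per half hour, each from 0.3 to 0.9. Here ρ is the correlation left after participant and meal effects are removed.

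**Step 1: subtract the fasting value, or adjust for it.**
- Variance of the change score: 2s²(1 − ρ).
- Variance of the adjusted 3-hour value: s²(1 − ρ²).
- Ratio: (1 + ρ)/2.

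| Pattern | Fasting to 3-hour correlation | Ratio | Reduction |
|---|---|---|---|
| Constant, 0.3 | 0.3 | 0.65 | 35% |
| Constant, 0.9 | 0.9 | 0.95 | 5% |
| Decaying, 0.3 | 0.3^8 ≈ 0.0001 | 0.50 | 50% |
| Decaying, 0.9 | 0.9^8 = 0.43 | 0.715 | 28% |

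Three qualifications apply.
- *Estimating the slope.* With participant and meal fitted, residual degrees of freedom are 30 − 1 − 9 − 2 = 18, and 17 with the covariate. Under normality, chance differences in fasting values inflate the variance of a meal contrast by 1 + 1/(18 − 2) = 1.0625 on average. The ratios 0.50, 0.65, 0.715 and 0.95 become 0.53, 0.69, 0.76 and 1.01, so the gain disappears at the last.
- *Unequal variances.* If the fasting SD is k times the 3-hour SD, the reduction is (k − ρ)²/(1 + k² − 2ρk). Before the slope cost this is never negative, but it is zero when k = ρ.
- *Person-by-meal variation.* It adds equally to both variances. For illustration, at ρ = 0.5 the variances are 1.00s² and 0.75s². Adding a further s² to each gives 1.75/2.00, a 12.5% reduction instead of 25%.

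**Step 2: mean of the 2, 2.5 and 3 hour samples against the 3-hour sample, both as change scores.**
- Constant correlation: variance ratio (1 + 1/3)/2 = 0.667 for any ρ, SE ratio 0.816.
- Decaying correlation: variance ratio [(3 + 4r + 2r²)/9 + 1 − 2(r^6 + r^7 + r^8)/3] / [2(1 − r^8)], which is 0.743 at r = 0.3, 0.844 at 0.8 and 0.837 at 0.9. The SE ratio is 0.86 to 0.92.

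Relative signal-to-noise is the share of the 3-hour effect that the mean keeps, divided by the SE ratio:

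| Assumed time course | Share kept | Constant | Decaying |
|---|---|---|---|
| Flat from 2 h | 1 | 1.22 | 1.09–1.16 |
| Linear rise from 0 h | (0.667 + 0.833 + 1)/3 = 0.833 | 1.02 | 0.91–0.97 |
| Linear rise from 1 h | (0.5 + 0.75 + 1)/3 = 0.75 | 0.92 | 0.82–0.87 |
| Rise at 3 h only | 1/3 | 0.41 | 0.36–0.39 |

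If both summaries are adjusted for the fasting value, the constant-correlation variance ratio is (1 + 3ρ)/[3(1 + ρ)]: 1.9/3.9 = 0.487 at ρ = 0.3 and 3.7/5.7 = 0.649 at 0.9. Signal-to-noise is then 1.24 to 1.43 for the flat course, 0.93 to 1.07 for a rise from 1 h, and 0.41 to 0.48 for a rise at 3 h only. The late mean still wins or loses according to the shape of the curve.

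**The case against.** A change from fasting at a prespecified time is a legitimate and simple endpoint. The study gathers pilot data, makes no power claim, and this endpoint is secondary. If gas appears late, the 3-hour value may be the most informative single reading. All of that stands, which is why the 3-hour value should remain the main summary.

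A reader might infer that the plan discards six of the seven samples. The text does not go that far. It names only fasting and 3 hours, but "Average difference between treatment means" does not say what is averaged, and the unnamed factors of the two-way analysis could include time. What can be said is that no use of the other samples is stated.

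A reader might also infer that the late mean should replace the 3-hour value, since it is less noisy. Lower noise is not a better marker if the signal shrinks too, and the documents give no time course to settle it.

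Nor does imprecision here distort a planned test of the third hypothesis, because the Statistics section sets out no analysis for it. The risk lies in interpretation.

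Finally, the rank test may have been chosen to guard against skewed data. A covariate model gives up some of that protection, so its residuals need checking.

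**Conclusion.** The point holds in a limited form. As written, the endpoint is a change score with the error of two single readings. Adjusting for the fasting value instead lowers within-visit variance by about 5 to 50% before the slope is paid for. After the average slope cost, this runs from no gain (constant correlation of 0.9) to about 47% (decaying correlation of 0.3). The range rests on equal variances and assumed correlations, and person-by-meal variation makes the total gain smaller.

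It would be tempting to express the precision of the late mean as extra participants. The documents do not support such a figure: it would count the noise removed, ignore any signal lost, and treat the within-visit part as the whole variance.

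**What to change.** In the Assessment of Efficacy table and the Statistics section:
- For each gas, compare meals on the 3-hour value, with participant, meal and that visit's fasting value in the model. Fit participant as a fixed effect so that the slope is estimated within participants.
- Take the pairwise meal comparisons from the same model. The Wilcoxon test on the 3-hour change can stay as a check if residuals are skewed.
- Prespecify the mean of the 2, 2.5 and 3 hour samples, adjusted in the same way, as a supporting analysis. State that it favours an effect already flat by 2 hours and cuts a rise seen only at 3 hours to one third.
- Say what the averaging in the outcome measure refers to, and what is done with the remaining samples.

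The bloating and satiety row has the same wording and schedule, so the use of its repeated scores should be stated too.

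The cost is analysis wording, one residual degree of freedom (18 to 17) and the average 6% slope inflation shown above. No sample or visit is added.
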